7.3 SECONDARY ENDPOINTS

Secondary endpoints are defined in Table 3 below. This study will also collect data relating to the health economics of the FIRM-guided procedure to conduct additional evaluations if primary endpoints are met.

Table 3 – Secondary Endpoints

Endpoint	Definition
Acute Effectiveness	
The acute success of FIRM-guided procedure is defined as elimination of the source of arrhythmias identified by FIRMap as indicated by;
 
 1. No evidence of the source on FIRMap immediately post-procedure, OR 2. Reduction of electrogram amplitude to <0.2mV in region designated by FIRMap

Table 4 – Additional Evaluations

Parameter	Definition
Total RF ablation time	Total RF ablation time as measured by total time of ablation lesion applications, from first ablation lesion to end of last lesion, will be documented. These values will be compared between the FIRM-guided and conventional ablation groups. If ablation for AT/atrial flutter is pursued, this ablation time will be documented separately
Repeat procedure and hospitalization	Any descriptive information regarding repeat procedures and re-hospitalizations will be compared between groups
Cumulative long-term freedom from AF	Cumulative long-term freedom from AF will be assessed at 12 months after the initial AF procedure but will permit results of repeat ablation
Cumulative long-term freedom from AF without use of anti-arrhythmic drugs	Cumulative long-term freedom from AF without use of anti-arrhythmic drugs will be assessed at 12 months after the initial AF procedure but will permit results of repeat ablation
Early Recurrence of AF/AT	Recurrences of sustained AF/AT in the first 3 months (blanking period).
Change in Atrial Function	Change in left atrial size and pulmonary vein inflow Doppler on echocardiogram (when available)
Change in Ventricular Function	Change in left ventricular ejection fraction and parameters of diastolic dysfunction (when available)
Quality of Life	Impact on quality of life, using patient-reported outcome instruments (EQ-5D and AFEQT), within treatment groups (change from pre-procedure to post-procedure follow-up timepoints) and between treatment groups. Analysis will be performed if primary endpoints are met.
Economic Analysis	Cost-effectiveness analysis based on clinical and patient-reported outcomes and resource utilization. Analysis will be performed if primary endpoints are met.

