3 PROTOCOL SYNOPSIS

Sponsor: Abbott Electrophysiology (Topera, Inc.)

Protocol Title: Randomized Evaluation of Atrial Fibrillation Treatment with Focal Impulse and Rotor Modulation Guided Procedures (REAFFIRM)

Planned Study Centers: Up to 25 centers in Europe and North America

Primary Objective:

Evaluate the safety and effectiveness of FIRM-guided procedures in addition to conventional ablation for the treatment of patients with de novo persistent atrial fibrillation (AF).

Secondary Objectives:

- Evaluate the acute effectiveness of FIRM-guided procedures in eliminating the source of arrhythmia.

Study Design:

This is a prospective, multicenter, randomized study to assess the safety and effectiveness of FIRM-guided procedures followed by conventional ablation including PVI versus a standard PVI procedure for the treatment of de novo persistent atrial fibrillation.

Sample Size:

A total of up to 350 subjects will be enrolled and equally (1:1) randomized between those undergoing conventional AF treatment with ablation, vs. those with FIRM-guided procedures followed by conventional AF ablation. Additionally, ablation of any atrial tachycardias (AT) and/or the cavotricuspid isthmus may be performed in those subjects with documented AT/atrial flutter.

Study Duration:

Subject participation will require up to 13 months. The follow-up assessments will occur at 7-10 days post-procedure, 1, 3, 6, and 12 months post-procedure.

Inclusion Criteria:

Subjects are required to meet the following inclusion criteria:

1. Male or female 18 – 80 years of age.
2. Experiencing at least two (2) documented episodes of persistent atrial fibrillation (including long standing persistent) during the 3 months preceding study entry with clinical indication for AF ablation per guidelines. At least one episode must be documented by rhythm strip or ECG.
3. Refractory, contraindicated, or intolerant to Class I or III anti-arrhythmic medications. Drug doses must be therapeutic and stable.
4. Oral anticoagulation required with either Novel Oral Anticoagulant (e.g. dabigatran, rivaroxaban, apixaban), Warfarin (therapeutic INR ≥ 2.0 for at least three weeks prior to randomization), or other similar standard-of-care oral anticoagulant therapy is required (aspirin is not considered similar) for those subjects who meet two or more of the following criteria:
 - a. Age 65 years or older
 - b. Diabetes
 - c. Coronary artery disease (CAD)
 - d. Congestive heart failure

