4.2 HYPOTHESIS

Focal Impulse and Rotor Modulation (FIRM) guided procedures will eliminate the source of clinical arrhythmias in subjects with indications for AF ablation procedures.

5 **STUDY OBJECTIVES**

The primary objective is to evaluate the safety and effectiveness of FIRM procedures in addition to conventional ablation for the treatment of persistent atrial fibrillation (AF).

The secondary objectives are: 1) to evaluate the acute success of FIRM-guided procedure in eliminating the source of arrhythmias, and 2) to evaluate quality of life outcomes.

6 **STUDY DESIGN**

The study is designed as a prospective, multicenter, randomized study to assess the safety and effectiveness of FIRM procedures followed by conventional ablation including PVI versus a standard PVI procedure for the treatment of de novo persistent atrial fibrillation.

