time. The patient may be either excluded from the study or maintained on oral anticoagulation for an additional period of at least 6 weeks and re-tested (TEE repeated) for thrombi.

- 12-Lead ECG within 72 hours of study procedure.
- Cardiac medications currently prescribed for the subject's daily medical therapy.
- Pre-procedure laboratory values per standard practice.
- Neurological Exam (if clinically indicated) if symptoms suggestive of neurologic disease, and is to be performed by the neurology medical staff.
- Prior to the procedure, subjects fitting the investigator's standard criteria for anticoagulation will have been orally anti-coagulated (in case of Warfarin, with therapeutic INR (≥ 2.0) for at least three weeks prior to randomization, or they may be placed on therapeutic doses of subcutaneous low-molecular-weight heparin (LMWH)). As dictated by center clinical practice, oral anti-coagulation will be discontinued and either subcutaneous LMWH or IV heparin will be substituted at therapeutic doses until the time of the procedure. At the investigator's discretion, dabigatran, rivaroxaban or apixaban will be withheld for 24 hr. prior to the procedure.
- It is highly recommended that antiarrhythmic medications be stopped at least 3 days prior to the procedure; amiodarone should be stopped 30 days prior to procedure. Antiarrhythmic medications can resume following the procedure, at the investigator's discretion.
- EQ-5D and AFEQT Quality of Life surveys.
- Pregnancy test to be performed for women of child bearing potential.

Each site will maintain a screening log noting the reasons for screening failures.

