16.2 Study Endpoints

A. Long-Term Effectiveness (Primary effectiveness endpoint)

Two endpoints will be used for long term effectiveness after the initial AF ablation procedure (only):

Single Procedure Freedom from AF/AT recurrence* at 3 months, and

Single Procedure Freedom from AF/AT recurrence* from 3-12 months after the initial AF ablation procedure.

Freedom from AF/AT recurrence is defined as no documented episodes of AF > 30 seconds with conventional non-invasive monitoring. In the case of a cardiac implanted electronic device (CIED), freedom from AF/AT recurrence is defined as no documented episodes of AF > 30 in a 48 to 72-hour window at the follow-up visits in addition to any symptomatic episodes with documented AF > 30 seconds. AT recurrence does not include episodes of CTI (cavotricuspid isthmus) dependent flutter.

The statistical hypothesis for this endpoint is operationalized as follows:

$H_0: p_E = p_C$

$H_A: p_E \neq p_C$

$\alpha =$ [REDACTED]

Where:

p_E = the proportion of "successes" in the FIRM arm

p_C = the proportion of "successes" in the conventional ablation control arm

The proportion of successes in each treatment arm shall be evaluated relative to their respective primary endpoint using both Chi-Square (Binomial, 1df) and by Kaplan-Meier survival estimation. Each evaluation will include 95% confidence intervals. Since there are multiple (dual) independent endpoints, each resulting p-value will be reported both as calculated, and the associated Hochberg corrected p-value.

B. Acute Effectiveness (Secondary effectiveness endpoint)

The acute success of FIRM-guided procedure is defined as elimination of the source of arrhythmias identified by FIRMap as indicated by;

1. No evidence of the source on FIRMap immediately post-procedure, OR
2. Reduction of electrogram amplitude to <0.2mV in region designated by FIRMap

The proportion of successes in each arm will be calculated as follows:

$$\frac{n}{N}$$

Where:

n = the total count of "successful" subjects in the arm in question

N = the total count of subjects for that arm in the ITT group

The statistical hypothesis for this endpoint is operationalized as follows:

$$H_0: p_E = p_C$$

$$H_A: p_E \neq p_C$$

$$\alpha = \text{[REDACTED]}$$

Where:

p_E = the proportion of "successes" in the FIRM arm

p_C = the proportion of "successes" in the conventional ablation control arm

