This endpoint will be evaluated using a Chi-Square test of independence, the proportions assumed to be binomial for each group.

C. Acute Safety (Primary safety endpoint)

The acute safety success of either treatment arm is defined as freedom from serious adverse events related to the procedure within ten (10) days of the index procedure. The proportion of successes in each arm will be calculated as follows:

$$\frac{n}{N}$$

Where:

n = the total count of subjects presenting freedom from serious adverse events related to the procedure within ten (10) days of the index procedure.

N = the total count of subjects in that arm in the ITT group

The statistical hypothesis for this endpoint is operationalized as follows:

$H_0: p_E = p_C$

$H_A: p_E \neq p_C$

Where:

p_E = the proportion of "successes" in the FIRM arm

p_C = the proportion of "successes" in the conventional ablation control arm

This endpoint will be evaluated using a Chi-Square test of independence, the proportions assumed to be binomial for each group.

D. Long-Term Safety (Primary safety endpoint)

Long-term safety is defined as freedom from procedure-related serious adverse events (SAEs) (including those related to repeat procedures) within one year of the initial procedure.

The statistical hypothesis for this endpoint is operationalized as follows:

$H_0: p_E = p_C$

$H_A: p_E \neq p_C$

$\alpha =$

Where:

p_E = the proportion of subjects free from serious adverse events related to the procedure (including from any repeat procedures required) within one year of the index procedure in the FIRM arm

p_C = the proportion of subjects free from serious adverse events related to the procedure (including from any repeat procedures required) within one year of the index procedure in the conventional ablation control arm

The proportion of events in each treatment arm shall be evaluated relative to their respective primary endpoint using both Chi-Square (Binomial, 1df) and by Kaplan-Meier survival estimation. Each evaluation will include 95% confidence intervals.

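### Quality of life is an unconditional secondary objective in Section 5, but Table 4 commits to analysing it only if the primary endpoints are met, and the synopsis and Table 3 omit it

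*Protocol*

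**What the plan says.** The protocol gives quality of life a different standing in different places.

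- **Section 5 (Study Objectives)** lists two secondary objectives: acute success of the FIRM-guided procedure, and "to evaluate quality of life outcomes". Neither carries a condition.
- **Section 3 (Synopsis)** lists one secondary objective: "Evaluate the acute effectiveness of FIRM-guided procedures in eliminating the source of arrhythmia". Quality of life is not mentioned anywhere in the synopsis.
- **Section 7.3** says "Secondary endpoints are defined in Table 3 below". Table 3 has a single row, acute effectiveness.
- **Section 7.3, Table 4 (Additional Evaluations)** holds the Quality of Life row. It names EQ-5D and AFEQT and sets out comparisons within treatment groups "and between treatment groups. Analysis will be performed if primary endpoints are met". The Economic Analysis row has the same condition: "Cost-effectiveness analysis based on clinical and patient-reported outcomes and resource utilization. Analysis will be performed if primary endpoints are met".
- **Section 16.2 B** labels acute effectiveness the secondary effectiveness endpoint and states its test without condition: "This endpoint will be evaluated using a Chi-Square test of independence, the proportions assumed to be binomial for each group".
- **Sections 10.1 B and 10.3 B to E** schedule "EQ-5D and AFEQT Quality of Life surveys" at baseline and at 1, 3, 6 and 12 months, again without condition.

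**The concern.** An objective is a question the trial undertakes to answer. Here, whether one of them is analysed depends on how the primary comparison turns out. If the primary endpoints are missed, nothing in the protocol commits the sponsor to analysing quality of life, so the choice would be made with the primary result known. That is a route to selective reporting.

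It also bites where the information is most useful. Section 4 gives relief of symptoms as one of the two aims of treatment, whereas the primary effectiveness endpoint counts documented episodes longer than 30 seconds. After a neutral rhythm result, patient-reported benefit or harm would help to interpret it. The primary analysis itself is not at risk.

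**Working it through.** **1. Status of the two secondary objectives, side by side**

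| Place | Acute effectiveness | Quality of life |
|---|---|---|
| Section 5 | Secondary objective, no condition | Secondary objective, no condition |
| Synopsis | Secondary objective | Absent |
| Table 3 | Secondary endpoint | Absent |
| Table 4 | Not listed | Additional evaluation, conditional |
| Section 16.2 | Hypothesis and test, no condition | Absent |

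One of the two objectives in Section 5 therefore depends on the primary result.

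**2. How far the condition reaches.** Table 4 has nine rows, and only two are conditional: Quality of Life and Economic Analysis. Ablation time, repeat procedures, cumulative freedom from AF, early recurrence and the echocardiographic changes have no such condition. In the Quality of Life row the condition governs whether the analysis is done at all. It covers change within each group as well as the comparison between groups. Controlling error for a formal claim would not require that much.

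**3. Whether the condition can be applied.** There are four primary endpoints: two for safety (Table 1) and two for effectiveness (Table 2). The effectiveness pair is joined by *or* in Table 2 and by *and* in Section 16.2 A. The safety hypotheses in Section 16.2 C and D test for a difference and give no criterion for success. The condition therefore has no single reading.

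**4. Data collected regardless**

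- Visit text (Sections 10.1 B and 10.3 B to E): 2 instruments × 5 visits = 10 questionnaires per subject.
- At the Section 6.1 maximum: 10 × 350 = 3,500.
- Table 5 also appears to mark both surveys at Day 7-10, which the Day 7-10 visit text omits. On that reading: 2 × 6 = 12 per subject, and 12 × 350 = 4,200. The lower count is used here.

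**5. Precision of the estimate that might not be reported.** For equal arms of size n and no covariate adjustment, the 95% confidence half-width for the between-arm difference in change, in SDs of the change score, is 1.96 × √(2/n).

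- n = 350/2 = 175, none missing: 1.96 × √(2/175) = 1.96 × 0.1069 = 0.210.
- n = 175 × 0.8 = 140, assuming 20% missing: 1.96 × √(2/140) = 1.96 × 0.1195 = 0.234.

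The protocol states no figure of its own on this point to reproduce.

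**The case against.** The strongest reply is that Section 5 is the outlier. The synopsis, Table 3 and Section 16.2 agree that acute effectiveness is the only secondary item, and Table 4 openly calls quality of life an additional evaluation. Gating such an item on the primary result, in writing and in advance, is a recognised hierarchical choice. Aligning Section 5 with the other places would remove the contradiction without touching any analysis. The wording is also *if*, not *only if*, so an analysis after a missed primary is not forbidden, and a statistical analysis plan may commit to one.

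Parts of this stand. The instruments and comparisons are prespecified, the text forbids nothing, and a gate is legitimate for a confirmatory claim. It is also true that the half-widths would hold for any continuous outcome at these sizes, that 175 per arm is a ceiling, and that neither figure says how likely non-reporting is.

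The rest does not answer the point. Downgrading Section 5 would cure the label and leave reporting of randomised data dependent on the result. A gate on performing any analysis, descriptive change included, goes beyond multiplicity control. A separate analysis plan could add a commitment, but it would not reconcile the protocol's own objectives, synopsis and tables.

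**Conclusion.** The concern holds. The protocol makes quality of life an objective without condition in Section 5, and then commits to its analysis only if the primary endpoints are met. The synopsis and Table 3 leave it out. One of two secondary objectives could go unanswered after a neutral or negative trial. At stake is an estimate with a half-width of roughly 0.21 to 0.23 SD, drawn from up to 3,500 scheduled questionnaires. Those figures assume full enrolment of 350 split equally, no covariate adjustment, and either no missing data or an assumed 20% missing. The finding itself rests on the text and does not depend on them.

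This should be corrected, but it is not critical: no primary estimate or error rate changes.

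**What to change.** - In Table 4, delete the condition from the Quality of Life row. State that change from baseline in EQ-5D and AFEQT by arm, and the between-arm difference with its 95% confidence interval, will be reported whatever the primary result.
- If a gate is wanted, confine it to a confirmatory quality-of-life claim and say which primary endpoints must succeed to open it.
- Give quality of life one status across Section 5, the synopsis and Tables 3 and 4.
- The Economic Analysis row may stay conditional.

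The cost is a few wording edits and a modest amount of extra analysis. No new data are needed and the primary analysis is untouched.

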8 SELECTION, DISCONTINUATION, AND WITHDRAWAL OF SUBJECTS

8.1 SELECTION CRITERIA

The criteria listed below shall be used to determine if a participant is eligible for entry into the study. A subject must meet ALL of the study inclusion criteria and NONE of the study exclusion criteria in order to be considered eligible for participation.

A. *Inclusion Criteria*

Subjects are required to meet the following inclusion criteria:

1. Male or female 18 – 80 years of age.
2. Experiencing at least two (2) documented episodes of persistent atrial fibrillation (including long standing persistent) during the 3 months preceding study entry with clinical indication for AF ablation per guidelines. At least one episode should be documented by rhythm strip or ECG. Persistent AF is defined as continuous AF that is sustained beyond seven days (long standing persistent is >12 months). Episodes of AF in which a decision is made to electrically or pharmacologically cardiovert the patient after ≥48 hours of AF, but prior to 7 days, should also be classified as persistent AF episodes.
3. Refractory, contraindicated, or intolerant to Class I or III anti-arrhythmic medications. Drug doses must be therapeutic and stable.
4. Novel Oral Anticoagulant (e.g. dabigatran, rivaroxaban, apixaban), Warfarin (therapeutic INR ≥ 2.0 for at least three weeks prior to randomization), or other similar standard-of-care oral anticoagulant therapy is required (aspirin is not considered similar) for those subjects who meet two or more of the following criteria:
 - a. Age 65 years or older
 - b. Diabetes
 - c. Coronary artery disease (CAD)
 - d. Congestive heart failure
 - e. Hypertension with systolic >165 mm Hg
5. Willingness and able to remain on anti-coagulation therapy for a minimum of 3 months post procedure for all subjects and at least 12 months post procedure if the patient is on anti-coagulation pre-procedure or has CHADS2 score ≥ 2.
6. Left atrial diameter < 6.0 cm via transthoracic echo; or <6.5 cm via CT or MRI up to 3 months pre-procedure with documented image of largest dimension, or intraprocedural ICE or atrial angiogram if CT/MRI not available.
7. Sustained AF (>5 min uninterrupted) during the electrophysiology procedure. If the subject is not experiencing spontaneous, sustained AF, it may be induced by burst pacing (typically from the coronary sinus) with or without isoproterenol infusion in conventional clinical fashion.

8. Women without childbearing potential, (surgically sterile or have been without a period for 12 months), or women of childbearing potential who are not pregnant per a serum HCG laboratory test.
9. Willingness, ability and commitment to participate in baseline and follow-up evaluations without participation in another clinical trial which may confound the results of this study, unless approved by the Sponsor.
10. Signed patient informed consent form.

B. *Exclusion Criteria*

Subjects must NOT meet any of the following exclusion criteria:

1. Presence of structural heart disease of clinical significance including:
 - a. Coronary artery disease with either:
 - i. Coronary artery bypass surgery (CABG) within the last 180 days (six months), or
 - ii. Stable/unstable angina or ongoing myocardial ischemia.
 - b. Congenital heart disease where either the underlying abnormality or its correction prohibits or increases the risk of ablation.
2. NYHA Class IV.
3. Ejection fraction < 35% (within previous 3 months).
4. Previous AF ablation.
5. History of myocardial infarction (MI) within the past three months.
6. Any concomitant arrhythmia or therapy that could interfere with the interpretation of the results from this study.
7. ASD closure device, LAA closure device, prosthetic mitral or tricuspid valve, and permanent pacemakers or defibrillator leads.
8. Untreatable allergy to contrast media.
9. Severe electrolyte abnormalities at time of the ablation procedure or atrial fibrillation secondary to electrolyte imbalance, thyroid disease, or reversible non-cardiac cause.
10. Atrial fibrillation from a reversible cause (e.g., surgery, hyperthyroidism, pericarditis).
11. Contraindication to Heparin and Warfarin/other novel oral anticoagulants (e.g. dabigatran, rivaroxaban, apixaban).
12. History of pulmonary embolus within one year of enrollment.
13. Acute pulmonary edema.
14. Atrial clot/thrombus on imaging such as on a trans-esophageal echocardiogram (TEE) performed within 72 hours of the procedure if deemed appropriate by investigator.
15. History of a cerebrovascular disease (including stroke or TIA).

16. Any anticipation of cardiac transplantation or other cardiac surgery within the next 12 months.
17. History of documented thromboembolic event within the past one year that affects the ability to perform the procedure.
18. Diagnosed atrial myxoma.
19. Significant pulmonary disease, (e.g. restrictive pulmonary disease, constrictive or chronic obstructive pulmonary disease) or any other disease or malfunction of the lungs or respiratory system that produces severe chronic symptoms and significantly increases risk to sedation or anesthesia.
20. Acute illness or active systemic infection or sepsis.
21. History of blood clotting abnormalities or bleeding abnormalities.
22. Life expectancy of less than 12 months.
23. Presence of intramural thrombus, tumor, or other abnormality that precludes catheter introduction or safe manipulation.

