Freedom from AF/AT recurrence is defined as no documented episodes of AF > 30 seconds with conventional non-invasive monitoring. In the case of a cardiac implanted electronic device (CIED), freedom from AF/AT recurrence is defined as no documented episodes of AF > 30 seconds in a 48 to 72-hour window at the follow-up visits in addition to any symptomatic episodes with documented AF > 30 seconds. AT recurrence does not include episodes of CTI (cavotricuspid isthmus) dependent flutter.

Refer to the Statistical Analysis Plan for details.

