10.1 SCREENING AND BASELINE

A. *Screening*

Patients at the investigational sites with persistent AF will be asked about their interest in study participation. For those patients who express an interest to participate, the inclusion/exclusion criteria will be reviewed against existing medical history and the results of any standard clinical work-up to assess preliminary eligibility. Potential patients who do not meet entrance criteria may, as appropriate, repeat screening evaluations at a later time for possible enrollment into the study.

B. *Baseline Assessment*

If the patient is not excluded on the basis of existing medical history and standard clinical work-up, the patient will be asked to provide informed consent to participate in the study. Baseline assessments include the following as shown in Table 5 – Schedule of Assessments.

- Determine study eligibility based on the requirements specified in the inclusion / exclusion criteria.
- Demographics.
- Medical history, including any hospitalizations or emergency room visits for episodes of all cardiac arrhythmias within six months of screening, all anti-arrhythmic drugs (AADs) and other cardiac medications.
- Reported incidence of at least two (2) documented episodes of persistent atrial fibrillation (AF) during the three months preceding trial entry (at least one episode should be documented by rhythm strip or ECG).
- Treatments administered for atrial fibrillation in the six months prior to enrollment, e.g., pharmacologic treatments and non-pharmacologic interventions. Medications should include dose and duration.
- Documentation of therapeutic International Normalization Ratio (INR) for three weeks prior to the procedure (if applicable per Inclusion Criteria) in cases of subjects taking warfarin.
- NYHA class.
- Current cardiac rhythm.
- Largest dimension left atrial diameter measured from transthoracic echo, cardiac CT or cardiac MR within the last 3 months with image documentation. Intracardiac echocardiographic measurement at the time of the procedure can alternatively be used to document this.
- Ejection fraction (EF) measured within the last 3 months or from the pre-procedure TEE or TTE.
- When clinically indicated, TEE will be performed within 72 hours prior to the ablation procedure. If any evidence of left atrial thrombus is discovered, then the ablation procedure will not be performed at that

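### Does asking for two documented episodes in 3 months shut out the long-standing persistent AF that inclusion criterion 2 names as eligible?

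*Protocol*

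**What the plan says.** The criterion appears in three places.

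- **Synopsis (section 3), inclusion criterion 2**, has the same core wording as section 8.1 and adds "At least one episode must be documented by rhythm strip or ECG".
- **Section 8.1 A, inclusion criterion 2**, requires "Experiencing at least two (2) documented episodes of persistent atrial fibrillation (including long standing persistent) during the 3 months preceding study entry", with "At least one episode should be documented by rhythm strip or ECG". It then gives the definition: "Persistent AF is defined as continuous AF that is sustained beyond seven days (long standing persistent is >12 months". A further sentence, beginning "Episodes of AF in which a decision is made to electrically or pharmacologically cardiovert the patient", classes AF cardioverted after at least 48 hours but before 7 days as a persistent episode.
- **Section 10.1 B, baseline assessment**, lists "Reported incidence of at least two (2) documented episodes of persistent atrial fibrillation (AF) during the three months preceding trial entry" and adds "at least one episode should be documented by rhythm strip or ECG". It omits the parenthesis about long-standing AF.

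Section 8.1 requires every inclusion criterion to be met. Section 8.3 treats a subject as enrolled only once that is so. Section 13.4 classes any eligibility deviation as major. Section 16.1 limits the primary analysis group to randomized subjects who met all criteria and had a mapping or ablation catheter inserted.

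**The concern.** The criterion seems to work against itself. Long-standing persistent AF is, by the protocol's definition, continuous for more than 12 months. If it is never interrupted it fills the 3-month look-back and gives one bout, while two are required. The same holds for continuous AF of 3 to 12 months. The cardioversion sentence in section 8.1 supports reading an episode as a bout with a beginning and an end. The endpoint definition also speaks of episodes, in "no documented episodes of AF > 30 seconds with conventional non-invasive monitoring".

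Two things could be at stake. Up to 25 sites might screen the same kind of patient differently, which would affect recruitment and generalizability. And a subject enrolled on the inclusive reading might later be judged ineligible on the literal one. That would be a major deviation under section 13.4 and, through the wording of section 16.1, could remove the subject from the primary analysis. The change from *must* in the synopsis to *should* in sections 8.1 and 10.1 looks like a further inconsistency about proof.

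**Working it through.** The protocol states no figure on this point, so there is none to reproduce. The check is a reading of the three statements, followed by a sensitivity calculation on assumed shares.

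**1. Count on the literal reading.** The look-back is 3 months, about 90 days. AF continuous through it is 1 bout, and 1 is below the required 2. This applies to AF of more than 12 months and to AF of 3 to 12 months. A patient whose AF was interrupted in the window, for example by cardioversion, and who then had a further qualifying episode reaches 2. So even the literal reading does not bar every patient with long-standing AF.

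**2. Intent.** The parenthesis in the synopsis and in section 8.1 names long-standing persistent AF as included. A reading that rejects most of the group the sentence admits is the less natural one. A site could instead take the count as AF documented on two occasions, and nothing in the text rules that out. Section 10.1 B leaves out the parenthesis, but it is a checklist restating the criterion and does not override section 8.1.

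**3. Endpoint wording.** The recurrence definition asks whether any AF longer than 30 seconds was documented, that is, none against some. It never has to separate one continuous bout recorded twice from two bouts, so it does not settle the counting.

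**4. Must and should.** Both criterion lists open by saying that subjects are required to meet what follows. All three places set the same minimum of one episode on rhythm strip or ECG. Asking for at least one in that form implies that the other may be documented differently. The difference is editorial.

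**5. Route to the analysis set.** Eligibility is determined at baseline (sections 8.3, 8.4 and 10.1 B), before randomization. No section provides for re-adjudicating criterion 2 afterwards. The eligibility clause in section 16.1 has an evident use for criterion 7, sustained AF during the procedure, which Table 6 in section 10.2 shows can only be verified in the laboratory. The per-protocol analysis, which drops major deviations, is exploratory and optional.

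**6. Size, on assumed shares only.** Inputs: 350 subjects at 1:1 (section 6.1), hence 175 per arm. Let s be the share whose eligibility depends on the reading; s is assumed and is not in the protocol. Subjects affected = 350 × s. If all were removed equally from both arms, the standard error would be multiplied by 1/√(1 − s).

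| Assumed s | Subjects affected | Remaining | SE ratio |
|---|---|---|---|
| 5% | 17.5 | 332.5 | 1/√0.95 = 1.026 |
| 10% | 35 | 315 | 1/√0.90 = 1.054 |
| 20% | 70 | 280 | 1/√0.80 = 1.118 |
| 30% | 105 | 245 | 1/√0.70 = 1.195 |

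For scale, with success assumed at 0.50 in both arms, the 95% half-width for the difference is 1.96 × √(0.5/n per arm). That is 10.5 percentage points at 175 per arm and 11.0 at 157.5 (s = 10%). These figures are worst cases: every affected subject would have to be enrolled on one reading and later removed on the other.

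**The case for a change.** The case for amending is that this cannot be left to the SAP. Eligibility is applied at screening from the protocol, and a SAP cannot tell a site whom to enrol. Intent alone does not tell a coordinator what record makes the second episode. Monitors check protocol compliance against source (section 13.2), so a literal reading could surface after enrolment, and sections 13.4 and 16.1 then attach consequences to it. One clarifying sentence would cost little.

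Part of this stands. The counting rule is unwritten, the gap is most open for continuous AF of 3 to 12 months, which the parenthesis does not mention, and sites could screen unevenly. The rest carries less weight. The route from a monitoring query to exclusion from the primary analysis is conjecture. Making the analysis group conditional on eligibility is a general feature of section 16.1 that touches every criterion, so its weight does not belong to this one. Applying a new counting rule to subjects already randomized could itself create post-randomization exclusions, in a trial whose protocol describes no blinding. The baseline records, which need only a reported count of two and one strip or ECG, may not show whether two recordings belong to the same bout.

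**Conclusion.** The ambiguity is genuine but minor: a missing counting rule, with the intended population visible in the criterion itself. Sites can fill it sensibly from that intent, and the trial's comparison stays sound as written. The criterion is a pre-randomization history item, identical in both arms, so uneven reading affects who is recruited and how far results generalize; no bias between arms is shown. Its size cannot be computed from the protocol, and the shares of 5% to 30% above are assumptions that cannot support a finding of harm.

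This conclusion rests on two conditions: eligibility under criterion 2 is settled at baseline, as sections 8.3, 8.4 and 10.1 B describe, and nobody later uses a literal count to take randomized subjects out of the section 16.1 group. If the protocol is being amended for other reasons, the three statements could be reconciled for future screening, with the rule left to the sponsor. The point does not warrant an amendment of its own.
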